#### Incomplete Adverse Event Resolution Date

- Do not impute if any resolution date is missing
- If the duration of AE is needed, the following approach may be considered:
  - If year is missing (or AE resolution date is completely missing): do not impute
  - If year is not missing but month and day are missing: impute December 31st for missing month and day
  - If year and day are not missing but month is missing: impute December for missing month
  - If *year* and *month* are not missing but *day* is missing: impute last day of the *month* for missing *day*.

### Incomplete CM or MH Onset Date

- 1. If year is missing (or CM/MH onset date is completely missing): do not impute
- 2. If *year* is not missing but *month* and *day* are missing: impute January 1st for missing *month* and *day*
- 3. If year and day are not missing but month is missing: impute January for missing month
- 4. If year and month are not missing but day is missing: impute 01 for missing day

### Incomplete CM or MH Resolution Date

• Do not impute if any resolution date is missing.

# 5.3. Multi-Center Studies

This is a multi-center study enrolling subjects from 12 US sites. The number of subjects per site might be small. Therefore, there are no analyses adjusting for sites.

# 5.4. Multiple Comparisons / Multiplicity

This trial plans to have only one hypothesis testing, which is for the primary efficacy endpoint. Therefore, multiple comparisons do not apply and there is no need to adjust for multiplicity.

# 5.5. Interim Analysis

Following the Santen Steering Committee' recommendation, no interim analysis is planned for this study.

# 6. STUDY POPULATION

# 6.1. Safety Population

The Safety Population will include all subjects who signed informed consent, met the eligibility criteria at baseline (Visit 2, Day 1), and received at least one dose of the study medication. The safety analyses will be performed on the Safety Population.

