9.3.1. Safety Population

The Safety Population will include all randomized subjects who received at least one dose of the study medication.

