9.3.2. Full Analysis Set

The Full Analysis Set (FAS) will include all randomized subjects who received at least one dose of study medications and provided at least one post-baseline efficacy measurement.

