9.3.3. Per-Protocol Set

Then Per-Protocol Set (PPS) is a subset of the FAS, restricted to the subjects who fulfill the protocol in terms of the eligibility, medications, and outcome measurement.

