# 6.2. Full Analysis Set

The Full Analysis Set (FAS) will include all Safety population who had at least one post-baseline DCNVA measurement. The efficacy analyses will be performed using the FAS or a subset of the FAS.

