# 6.3. Per-Protocol Set

The Per-Protocol Set (PPS) is a subset of the FAS, restricted to the subjects who fulfill the protocol in the terms of eligibility, interventions, and other assessment. It will be the analysis population for some sensitivity analyses.

Before database lock, Santen's study team will review all protocol deviations, identify subjects with any protocol deviation that could impact the efficacy outcome, and determine whether to exclude the subject from the PPS.

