## 7.4. **Protocol Deviations**

In this study, protocol deviations are categorized as follows:

- Informed Consent
- Inclusion/Exclusion Criteria
- Concomitant Treatment
- Investigational Product
- Procedures/Tests/Assessments
- Laboratory
- Time Window
- Other

A protocol deviation is considered significant if it may affect the subject's rights, safety, or well-being, and/or the completeness, accuracy, or reliability of the study data. Santen's study team will review all protocol deviations and determine the list of significant protocol deviations prior to database lock. All FAS subjects with any significant protocol deviation(s) will be tabulated by deviation category for each planned treatment and overall. In addition, two listings will be provided: (1) all significant protocol deviations and (2) subjects excluded from the per protocol population.

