# 7.8. Exposure to Study Medication

The duration of exposure to a study medication is measured by days on treatment as derived in Section 4.5. For subjects in the Safety Population, the duration of exposure will be summarized using descriptive statistics, and frequency and percentage of subjects will be tabulated by duration category (1-30 days, 31-60 days, or  $\geq 61$  days) for each actual treatment received.

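### The SAP adds an eligibility condition to the Safety Population, and through it to the Full Analysis Set, that the protocol does not have and that SAP Section 10, as shown, does not declare

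*SAP*

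**What the plan says.** Protocol 9.3.1: "The Safety Population will include all randomized subjects who received at least one dose of the study medication". Protocol 9.3.2 defines the FAS as "all randomized subjects who received at least one dose of study medications and provided at least one post-baseline efficacy measurement". Eligibility first enters in protocol 9.3.3, where the Per-Protocol Set (PPS) is "restricted to the subjects who fulfill the protocol in terms of the eligibility, medications, and outcome measurement".

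SAP 6.1 defines the Safety Population as subjects who signed consent, "met the eligibility criteria at baseline (Visit 2, Day 1), and received at least one dose of the study medication". The word *randomized* is absent and the eligibility condition is new. SAP 6.2 then states: "The Full Analysis Set (FAS) will include all Safety population who had at least one post-baseline DCNVA measurement". SAP 6.3 applies eligibility once more for the PPS, which is "restricted to the subjects who fulfill the protocol in the terms of eligibility, interventions, and other assessment".

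The Safety Population is the basis for all safety summaries (SAP 9.1.2) and for exposure (SAP 7.8): "For subjects in the Safety Population, the duration of exposure will be summarized using descriptive statistics". The FAS or a subset of it is the basis for the efficacy analyses (SAP 6.2).

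**The concern.** A safety set should hold everyone who was exposed. An eligibility breach that comes to light after dosing is the case in which the subject most needs to stay in the denominator. As SAP 6.1 is written, that subject's adverse events and exposure would be missing from the summary tables. Because SAP 6.2 inherits the condition, the primary analysis would also use a narrower set than the protocol's FAS.

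The SAP states that it applies to the original protocol of 23 September 2022, so an amendment does not explain the difference. Two programmers could read the clause differently and produce different denominators.

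A second, smaller difference is that SAP 6.2 asks for a post-baseline DCNVA measurement where the protocol asks for any efficacy measurement.

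**Working it through.** **Step 1: the definitions side by side**

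| Set | Protocol | SAP |
|---|---|---|
| Safety | Randomized; at least one dose | Consent; eligible at Visit 2; at least one dose |
| FAS | Randomized; at least one dose; a post-baseline efficacy measurement | SAP Safety Population; a post-baseline DCNVA measurement |
| PPS | FAS, with eligibility, medication and outcome conditions | FAS, with eligibility, intervention and assessment conditions |

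**Step 2: is the change declared?** SAP Section 10 as shown covers the responder definition, two added safety endpoints, the 95% threshold and observed-case analysis. The SAP contents list shows no Section 10 heading on analysis populations. Parts of Section 10 are blank in the public copy, so a sentence there cannot be ruled out.

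**Step 3: fit with the rest of the SAP.** If eligibility is already required for the FAS, applying it again in SAP 6.3 is largely redundant. SAP 7.4 says "All FAS subjects with any significant protocol deviation(s) will be tabulated by deviation category for each planned treatment and overall", and its categories include one for inclusion and exclusion criteria; on the literal reading that row would be close to empty. This is a tension and not a strict contradiction. The clause is tied to Visit 2, some restrictions in protocol 6.5.1 run through the whole study, and a category may have no entries.

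**Step 4: what a literally excluded subject loses.** The subject would leave the adverse-event, other safety and exposure summaries and the primary analysis. The subject would still appear in the disposition of all randomized subjects (SAP 7.1), and the individual-data and adverse-event listings (SAP 5, 9.2) would still show the events.

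**Step 5: size per subject**

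- Inputs: 30, 30 and 15 subjects and SD 6 letters (SAP 3.3); historical control n = 23, SD 4.35 letters (SAP 8.2.1). The borrowing weight w is not shown, so a range is used.
- Share of the safety denominator: 1/15 = 6.7%; 1/30 = 3.3%; 1/75 = 1.3%.
- SE of the active-minus-placebo difference before borrowing: 6 × √(1/30 + 1/15) = 1.897 letters.
- Omitting one subject who lies d letters from the mean of the others moves that arm's mean by d/n. The deviations are assumed.
  - Placebo, 0.5 SD: 3/15 = 0.2 letters (0.11 SE).
  - Placebo, 1 SD: 6/15 = 0.4 letters (0.21 SE).
  - Placebo, 2 SD: 12/15 = 0.8 letters (0.42 SE).
  - Active, 1 SD: 6/30 = 0.2 letters (0.11 SE).
- With borrowing, prior precision is p = w × 23/4.35² = 1.2155w and placebo data precision is 15/36 = 0.4167. Taking the historical mean equal to the mean of the other 14, the 1-SD placebo shift is (6/36)/(p + 0.4167), and the SE of the difference is √(36/30 + 1/(p + 0.4167)).

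| w | Shift (letters) | SE (letters) | Shift / SE |
|---|---|---|---|
| 0 | 0.400 | 1.897 | 0.21 |
| 0.25 | 0.231 | 1.609 | 0.14 |
| 0.5 | 0.163 | 1.475 | 0.11 |
| 1 | 0.102 | 1.346 | 0.08 |

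**Step 6: power.** Without borrowing (difference 4 letters, SD 6, one-sided 0.05), power is 67.8% with nobody excluded. At assumed exclusion shares of 2%, 5% and 10%, applied equally to each arm, it is 67.1%, 65.9% and 63.9%.

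**The case against.** The strongest reply is that SAP 6.1 merely recounts subject flow: consent, eligibility at Visit 2, first dose. Elsewhere eligibility is the gate to randomization. Footnote i of SAP Table 2 says only eligible patients are enrolled and dosed, protocol 5 bars waivers, and protocol 5.1 reconfirms the acuity criteria at Visit 2. The only subject-level exclusion review the SAP describes is in 6.3, for the PPS. On this reading the clause stands in for *randomized*, and the two documents select the same subjects apart from the DCNVA wording.

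This reading is plausible and limits how often the clause could matter. It does not settle the point. Some restrictions rest on history, such as medical therapy for presbyopia within 30 days of screening or any contact lens use, and a breach can surface after dosing. If the clause only describes flow, it should not be a condition in a set definition.

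Two lesser objections largely stand. The missing word *randomized* adds little by itself, because SAP 4.1 and SAP Table 3 tie baseline and first dose to randomization. The DCNVA wording does not touch the primary analysis, which uses observed DCNVA cases (SAP 5.2.1); DCNVA is scheduled at every visit, and naming the qualifying measurement can be seen as ordinary SAP detail. It is still a difference from the protocol that one line would record.

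**Conclusion.** The concern holds. On the text, SAP 6.1 and 6.2 define narrower sets than protocol 9.3.1 and 9.3.2, and Section 10 as shown does not declare it. That part is certain, subject to the blank parts of Section 10. Whether anyone is excluded depends on how the clause is programmed and on whether an ineligible subject was dosed; the documents report no such subject.

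The main consequence is for the safety tables, where the small placebo arm makes a single omission visible. The shift and power figures rest on assumed deviations, assumed exclusion shares and an unseen w, and they point to a small effect on the primary result. This should be fixed because the rule as written can give wrong safety denominators and the repair is nearly free.

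**What to change.** - **SAP 6.1:** restore the protocol 9.3.1 definition: all randomized subjects with at least one dose, and no eligibility condition.
- **SAP 6.2:** define the FAS directly as randomized, dosed subjects with at least one post-baseline DCNVA measurement and record that narrowing in Section 10, or use the protocol's broader efficacy wording.
- **SAP 6.3:** leave eligibility here, as the only set to which it applies.
- **If the eligibility condition is intended:** declare and justify it in Section 10.

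The cost is two sentences in SAP 6.1 and 6.2, one line in Section 10 if DCNVA is kept, and a check of the population flags in programming.

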# 6.2. Full Analysis Set

The Full Analysis Set (FAS) will include all Safety population who had at least one post-baseline DCNVA measurement. The efficacy analyses will be performed using the FAS or a subset of the FAS.

# 6.3. Per-Protocol Set

The Per-Protocol Set (PPS) is a subset of the FAS, restricted to the subjects who fulfill the protocol in the terms of eligibility, interventions, and other assessment. It will be the analysis population for some sensitivity analyses.

Before database lock, Santen's study team will review all protocol deviations, identify subjects with any protocol deviation that could impact the efficacy outcome, and determine whether to exclude the subject from the PPS.

# 7. SUMMARY OF STUDY POPULATION DATA

## 7.1. Subject Disposition

The disposition of all randomized subjects will be summarized by treatment and overall. The summary will include the number and percentage of subjects in the Safety population, FAS, and PPS. The disposition summary will also include the number and percentage of subjects who completed the treatment period, who completed all study visits, subjects who discontinued the study prematurely before the end of treatment period (Visit 6, Month 2), as well as the number and percentage of subjects who discontinued from the study prior to Month 3 Visit by the primary discontinuation reason separately.

# 7.2. Demographics and Baseline Characteristics

Subject demographics and baseline characteristics will be descriptively summarized for FAS. Specifically, for subject demographics, the following variables will be summarized:

- Age at enrollment (continuous and categorical: 47-50 years or 51-55 years)
- Sex (categorical: Male or Female)
- Ethnicity (categorical: Hispanic/Latino or Not)
- Race (categorical: American Indian or Alaska Native, Asian, Black or African American, Native Hawaiian or Other Pacific Islander, White, or Other)

For baseline characteristics, the following variables will be summarized for both eyes (if applicable), study eye and fellow eye, separately:

- Best corrected distance visual acuity
- •
- Distance corrected near visual acuity
- Objective refraction (spherical/cylinder/axis)
- Subjective refraction (spherical equivalent, spherical, cylinder, and axis)
- Refractive status (categorical: Myopes/Emmetropes/Hyperopes)

# 7.3. Medical and Surgical History

For this study, medical and surgical history and adverse events will be coded using MedDRA 25.1, September 2022. Each medical event will be classified into a system organ class (SOC) and mapped to a Preferred Term (PT).

The medical and surgical history will be summarized for the FAS population. Subjects reporting any medical and surgical history at baseline will be tabulated by SOC and PT for each planned treatment and overall.

## 7.4. **Protocol Deviations**

In this study, protocol deviations are categorized as follows:

- Informed Consent
- Inclusion/Exclusion Criteria
- Concomitant Treatment
- Investigational Product
- Procedures/Tests/Assessments
- Laboratory
- Time Window
- Other

A protocol deviation is considered significant if it may affect the subject's rights, safety, or well-being, and/or the completeness, accuracy, or reliability of the study data. Santen's study team will review all protocol deviations and determine the list of significant protocol deviations prior to database lock. All FAS subjects with any significant protocol deviation(s) will be tabulated by deviation category for each planned treatment and overall. In addition, two listings will be provided: (1) all significant protocol deviations and (2) subjects excluded from the per protocol population.

# 7.5. Impact of the COVID-19 Pandemic

The impact of the COVID-19 pandemic is defined as any disruption to the study and subject participation, such as changes in study visits, missed visits, subject discontinuations, etc. All Safety Population subjects who experienced any of such impact will be summarized and listed along with the description of how their participation was altered.

# 7.6. **Prior and Concomitant Medications**

Non-study medications will be categorized into prior medications and concomitant medications. Specifically, *prior medication* is defined as any non-study medication taken and ended prior to the study medication start date. *Concomitant medication* is defined as any non-study medication taken concurrently while receiving study medication, i.e., the period from first dose to last dose of a concomitant medication taken by a subject must overlap with the period from first dose to last dose to last dose of the study medication.

For this study, non-study medications, including prior and concomitant medications, will be coded using World Health Organization (WHO) Drug Global, Version September 2018, format B3. Each non-study medication will be classified using the Anatomical-Therapeutic-Chemical (ATC) classification system and mapped to a WHO Drug preferred drug name.

Non-study medications will be summarized for the Safety population. Subjects taking any prior medications will be tabulated by ATC level 3, level 4, and preferred drug name. A subject will be counted at most once for each prior medication, even if the subject took the same prior medication on multiple occasions. Subjects taking any concomitant medications will be tabulated similarly. In addition, prior medications and concomitant medications will also be listed, separately.

# 7.7. Treatment Compliance

For compliance calculation, there will be three study intervals in the Treatment Period:

- Baseline Visit to Day 7
- Day 7 to Day 14
- Day 14 to Month 1
- Month 1 to Month 2

The compliance rate for a subject will be calculated as follows for each study interval:

Compliance Rate (%) =  $(2 \text{ x Duration} - \sum \text{Miss}) / (2 \text{ x Duration}) \times 100$ 

Where

Duration: The number of days subject should have administered study medication calculated as:

Study Interval	Equation for Duration Calculation
Baseline to Day 7	Day 7 Visit date – Date of first study drug dispensation
Day 7 to Day 14	Day 14 Visit date – Day 7 Visit date
Day 14 to Month 1	Month 1 Visit date – Day 14 Visit date
Month 1 to Month 2	Month 2 Visit date – Month 1 Visit date

Miss: The number of missed doses since the last visit.

A subject is fully compliant with the study treatment if his/her overall compliant rate is 100% over the Treatment Period (between Baseline and Month 2). The compliance rate of subjects in the FAS will be summarized by study intervals and over the Treatment Period for each planned treatment and overall.

# 7.8. Exposure to Study Medication

The duration of exposure to a study medication is measured by days on treatment as derived in Section 4.5. For subjects in the Safety Population, the duration of exposure will be summarized using descriptive statistics, and frequency and percentage of subjects will be tabulated by duration category (1-30 days, 31-60 days, or  $\geq 61$  days) for each actual treatment received.

# 8. EFFICACY ANALYSES

### 8.1. Efficacy-Related Definitions

#### 8.1.1. Study Eye and Fellow Eye

The *study eye* of a treated subject will be the eye that received the study medication and has a lower score of DCNVA as study eye at Visit 2 (Baseline, Day 1). If both eyes have the same score of DCNVA, the right eye will be designated as the study eye. The other eye will be the non-study eye, or *fellow eye*.

#### 8.1.2. Baseline Score

The *baseline score* is the observed measurement at Visit 2 (Baseline, Day 1). If a baseline score is missing, the last observed measurement or derived score prior to the first dose of study medication will be used to impute the baseline score.

#### 8.1.3. Change and Percent Change from Baseline

The change and the percent change from baseline in a measure at a post-baseline visit will be derived as:

- Change = (Score at the Post-Baseline Visit) (Baseline Score)
- Percent Change from Baseline =  $100 \times$  Change / (Baseline Score)

#### 8.1.4. Efficacy Measures

Table 5 lists all the efficacy measures that will be evaluated in this study.

Efficacy Measures	Note
Distance-corrected Near Visual Acuity (DCNVA)	DCNVA will be measured in the right eye, left eye and both eyes at all visits using the distance manifest refraction. The total number of letters at 40 cm will be recorded.
Near Activity Visual Questionnaire (NAVQ): Rasch score and overall satisfactory score	Any N/A responses are scored according to the median overall score. The summated score from the main body of 10 questions is adjusted to a Rasch score from 0 to 100 using a conversion table (Section 12.1) such that 0 indicates no difficulty at all with any near tasks, and 100 indicates extreme difficulty with all near activities.

#### Table 5:Efficacy Measures

Efficacy Measures	Note
Patient Global Rating of Treatment	At Visit 6 (month 2), patients will be asked to rate their overall satisfactory with the treatment on a 4-point Likert scale with responses including 'Unsatisfactory', 'Not very satisfactory', 'Satisfactory', and 'Very satisfactory'.
Objective and Subjective Refraction	Objective refraction will be performed as per standard of care using autorefractor available at clinical site at all study visits. Subjective refraction with "push plus" approach will be performed at all visits to determine the best correction for a subject to perform the visual acuity tests.

 Table 5:
 Efficacy Measures (Continued)

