8.1.6. Double-Masked Treatment Period, Visit 6 (Month 2)

- •
- Measure vital signs
- Update concomitant medications and procedures/therapies
- •

- •
- Measure vital signs
- Update concomitant medications and procedures/therapies

- Perform slit-lamp Biomicroscopy
- Measure pupil size
- Measure Intraocular Pressure
- •
- •
- Obtain urine and perform a urine pregnancy test if the subject is a female of child-bearing potential.
- Assess for adverse events
- Exit the subject from the study.

NOTE:

If the study medication administration is discontinued, then to the extent possible, all procedures for Study Exit/Early Termination as per SoA (Table 2) will be performed on the day of early termination. Subjects who are discontinued from the study early will not be replaced.

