#### 2.2.2. Secondary Efficacy Endpoints

- Mean change from baseline in Study Eye DCNVA at all visits
- Mean change from baseline in Binocular DCNVA at all visits
- Proportion of subjects who improve 1/2/3-lines or more in Study Eye and Binocular DCNVA at each visit without loss of more than 1 line (5 letters) in Best Corrected Distance Visual Acuity (BCDVA)
- Mean change from baseline in quality of life assessed with Near Activity Visual Questionnaire (NAVQ) at Month 2 and Month 3
- Subject treatment satisfaction as assessed by Patient Global Rating of Treatment at Month 2

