# **3.4.** Visits and Assessments

There are 7 scheduled visits for each enrolled subject. Assessments at each visit and the time/visit window for each post-baseline assessment are specified in the Assessment Schedule (Table 2). For subjects whose study participation is terminated prior to Visit 7 (Month 3), to the extent possible, all assessments scheduled for Visit 7 (Month 3) will be performed at the Exit Visit.

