### Table 2:Assessment Schedule

		Treatment Period				Follow Up Without Treatment	
Study Procedures	Visit 1 / Screening Up to 15 days before Day 1	Visit 2 Baseline / Day 1	Visit 3 Day 7 ± 2 days	Visit 4 Day 14 ± 2 days	Visit 5 Month 1 ± 3 days	Visit 6 Month 2 ± 3 days	Visit 7 Month 3 ± 3 days / Early Discontinuation
Informed consent a	Х						
Inclusion and Exclusion criteria	Х	Х					
Symptom Assessment iN Dry Eye questionnaire (SANDE) b	X						
Near Activity Visual Questionnaire (NAVQ) b		Х				Х	Х
Demographics information	Х						
Ocular and systemic medical history	Х						
Vital signs (blood pressure, heart rate, temperature)	Х	Х	Х	X	Х	Х	Х
Height and weight	Х						
Previous and current concomitant ocular and systemic medications	Х	Х	Х	X	Х	Х	Х
Objective refraction test	X c	Х	Х	Х	Х	Х	Х
Subjective refraction test	X	Х	X	X	Х	Х	X
Distance Corrected Near Visual Acuity (DCNVA) test d	X	X	X	X	X	X	X

		Treatment Period					Follow Up Without Treatment
Study Procedures	Visit 1 / Screening Up to 15 days before Day 1	Visit 2 Baseline / Day 1	Visit 3 Day 7 ± 2 days	Visit 4 Day 14 ± 2 days	Visit 5 Month 1 ± 3 days	Visit 6 Month 2 ± 3 days	Visit 7 Month 3 ± 3 days / Early Discontinuation
Best Corrected Distance Visual Acuity (BCDVA) test d	Х	Х	Х	Х	Х	Х	Х
Slit lamp biomicroscopy	Х	Х	Х	Х	Х	Х	Х
Pupil size	Х	Х	Х	Х	Х	Х	Х
Tear film break-up time (TFBUT)	Х						
Corneal Fluorescein Staining (CFS) assessment (with Oxford Scale)	Х						
Intraocular pressure (IOP)	Х	Х	Х	Х	Х	Х	Х
Ophthalmoscopy	X g	Х	Х	Х	Х	Х	X g
Patient global rating of treatment						Х	
Post-study clinical trial experience survey							Х
Urine pregnancy test (women of childbearing potential only) h	Х					Х	Х
Blood chemistry and Hematology (CBC, CMP)	Х				Х	Х	
Hemoglobin A1c	Х						
Urinalysis	X				Х	Х	

		Treatment Period				Follow Up Without Treatment	
Study Procedures	Visit 1 / Screening Up to 15 days before Day 1	Visit 2 Baseline / Day 1	Visit 3 Day 7 ± 2 days	Visit 4 Day 14 ± 2 days	Visit 5 Month 1 ± 3 days	Visit 6 Month 2 ± 3 days	Visit 7 Month 3 ± 3 days / Early Discontinuation
Adverse events (AEs)	X	Х	Х	Х	Х	Х	Х
Dispense study medication		X i			Х		
Medication compliance diary j			Х	Х	Х	Х	

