# 5.2. Handling of Missing Data

#### 5.2.1. Efficacy Measures

The primary analysis of DCNVA will be based on observed cases; hence, missing data will not be imputed. As a sensitive analysis of the primary efficacy endpoint, an analysis using mixed-effect model for repeated measures (MMRM) will be performed. The MMRM model will be applied using observed cases and no imputation will be needed.

For continuous secondary endpoints where MMRM-based analysis will be performed, no imputation will be necessary. For binary secondary endpoints with response status, the analysis will be based on observed cases; hence, no imputation will be performed.

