### 8.3.2. Analyses of Binary Secondary Endpoints

The following binary secondary endpoints will be summarized descriptively:

- Having Binocular DCNVA 1/2/3-line gain from baseline at each visit
- Having Study Eye DCNVA 1/2/3-line gain from baseline at each visit
- Proportion of subjects with treatment satisfactory assessed by Patient Global Rating of Treatment at Month 2

The responder rates will be tabulated using frequencies and percentages based on observed cases.

For exploratory purposes, comparison between 0.1% STN1013600 vs Placebo and between 0.3% STN1013600 vs Placebo in response rate will be performed using the Fisher's Exact test for a 2x2 contingency table.

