#### **10.1.3.** Exploratory endpoints

# **10.2. Primary Analysis**

In the protocol, the superior of the treatment arm over placebo arm would be establish of the probability of (Treatment mean – Placebo mean > 0) given the data is greater than 90%. In this SAP, the criterion was revised to be more stringent with 95% will be used to establish the superior of the treatment over the placebo. The new threshold of 95% will guarantee the (Bayesian) type I error to be lower than or equal to 0.10.

Analysis will be based on observed cases instead of multiple imputation approached imputed values due to the following rationales:

• In general, discrepancy in analysis results due to different imputation approaches are minimal when the amount of missing data is small. Based on masked review of subject disposition, few of than 5% of subjects with missing data due to missed visits and premature study discontinuation.

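### The satisfaction proportion covers only subjects who attend Visit 6, because the Patient Global Rating is not scheduled at early discontinuation

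*SAP*

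**What the plan says.** Treatment satisfaction is a named secondary efficacy endpoint in SAP Section 2.2.2: "Subject treatment satisfaction as assessed by Patient Global Rating of Treatment at Month 2". Table 5 gives the time of collection: "At Visit 6 (month 2), patients will be asked to rate their overall satisfactory with the treatment on a 4-point Likert scale". In SAP Table 2 the row "Patient global rating of treatment" has one mark, under Visit 6, and none under Visit 7/Early Discontinuation.

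For subjects who end participation before Visit 7, SAP Section 3.4 says that, as far as possible, "all assessments scheduled for Visit 7 (Month 3) will be performed at the Exit Visit". The protocol's note on stopping study medication, at the end of the Visit 7 list (Section 8.1.7), says that "all procedures for Study Exit/Early Termination as per SoA (Table 2) will be performed on the day of early termination". Neither route includes the rating.

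On analysis, SAP Section 5.2.1 states: "For binary secondary endpoints with response status, the analysis will be based on observed cases; hence, no imputation will be performed". Section 8.3.2 repeats this for the tables: "The responder rates will be tabulated using frequencies and percentages based on observed cases". That section adds exploratory Fisher's exact comparisons of each active arm with placebo.

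In SAP Table 4, the Month 2 window for the rating is [2, -], that is, from Day 2 with no upper limit.

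**The concern.** The FAS in SAP Section 6.2 needs only one post-baseline DCNVA measurement. A subject who exits after Day 7 and before Visit 6 is therefore in the FAS but has no scheduled rating, and the observed-case rule takes that subject out of the satisfaction denominator. The same happens to a subject who misses Visit 6 and returns for Visit 7.

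This matters more for satisfaction than for most measures, because dissatisfaction is a plausible reason to leave and missing ratings may not be a random subset. The primary endpoint has an MMRM and a per-protocol repeat as sensitivity analyses. This endpoint has none. What is at stake is the descriptive satisfaction rate in each arm and the exploratory comparison between arms, not the primary conclusion.

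**Working it through.** The plan gives no figure for this endpoint, so there is none to reproduce. The check is a cross-reading followed by a size estimate.

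**Inputs**
- Arm sizes of about 30, 30 and 15 (SAP Section 3.3).
- Missing data from a masked disposition review: "few of than 5% of subjects with missing data due to missed visits and premature study discontinuation" (SAP Section 10.2), read here as fewer than 5%.
- Satisfaction rate: not in the documents. I assume 60% and show 40% and 80% as a range.

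**Step 1: who can be unrated.** The rating is at Visit 6 only, the early-exit assessments omit it, and nothing is imputed. The denominator is therefore the subjects who attended Visit 6 and answered.

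**Step 2: how many.** 5% of 75 = 3.75. Since 3/75 = 4.0% and 4/75 = 5.3%, at most 3 subjects lie below 5%.

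**Step 3: bias.** Let n be the arm size, m the number unrated, p_obs the rate among those rated and p_m the rate the unrated would have given. The full-arm rate is [(n − m) × p_obs + m × p_m] / n, so

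observed rate − full-arm rate = (m/n) × (p_obs − p_m).

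The bias is zero if the unrated are as satisfied as the rated, and positive if they are less satisfied.

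**Step 4: one dissatisfied leaver (m = 1, p_m = 0), full-arm rate 60%.**
- Placebo: 9/15 = 60.0% is reported as 9/14 = 64.3%, a shift of 4.3 points.
- Active arm: 18/30 = 60.0% is reported as 18/29 = 62.1%, a shift of 2.1 points.

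The numerator does not change, because a dissatisfied subject was never in it.

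**Step 5: outer bounds, all 3 unrated subjects in one arm.** The lower bound is p_obs × (n − m)/n and the upper bound is [p_obs × (n − m) + m]/n. For 60% on placebo these are 0.6 × 12/15 = 48% and (7.2 + 3)/15 = 68%. For 60% on an active arm they are 0.6 × 27/30 = 54% and (16.2 + 3)/30 = 64%.

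| Observed rate (assumed) | Active arm, 27 of 30 rated | Placebo, 12 of 15 rated |
|---|---|---|
| 40% | 36% to 46% | 32% to 52% |
| 60% | 54% to 64% | 48% to 68% |
| 80% | 72% to 82% | 64% to 84% |

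The products are not all whole subjects, so the bounds are illustrative.

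**The case against.** The strongest reply is that little depends on this. SAP Section 5.4 declares one hypothesis test, for the primary endpoint. Satisfaction is summarized descriptively, and its Fisher's tests are exploratory. The under-5% figure combines missed visits and discontinuations for any reason, and some of those subjects may have left after Visit 6, so 3 is a ceiling. SAP Section 7.1 already tabulates by treatment the discontinuations before Visit 6. All of this stands and sets the priority. However, the disposition table covers all randomized subjects and does not show how many FAS subjects lack a rating.

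A reader might infer from the Day 2 window that an exit rating was planned and then forgotten. The documents do not support that. SAP Section 4.4 says the windows are there to limit missing data, and a measure taken once after baseline can have every post-baseline value mapped to its only visit. Laboratory tests have a similarly wide Month 1 window, [2, 49], and are not scheduled at early discontinuation either. The window shows only that an exit rating, if collected, would be assigned to Month 2.

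A reader might also infer that everyone who stops the drops goes unrated. Protocol Section 7.1 has assessments continue per the schedule after study medication is stopped, so such a subject could still attend Visit 6. The Section 8.1.7 note points instead to exit procedures on the day of early termination. The documents do not settle this, and the accurate condition is attendance at Visit 6.

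The remedy is also open to challenge. A rating given at exit is not satisfaction at Month 2, and counting every missing rating as not satisfied treats administrative or COVID-19 misses as dissatisfaction. Both points are fair, which is why the added row should supplement the planned table and not replace it.

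Finally, protocol Section 10.4.17 has no visible text and parts of the visit lists are blank, so an instruction there cannot be excluded. The visible schedules and SAP Table 5 agree with each other.

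**Conclusion.** The point holds as a low-priority improvement. On the visible text, the satisfaction proportion is conditional on attending Visit 6, and FAS subjects who exit earlier drop out of the denominator.

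Whether this overstates satisfaction depends on an assumption the documents cannot confirm: that unrated subjects are less satisfied than rated ones. It would be tempting to say that the rate is inflated, and more so in the arm with more treatment-related exits. The visible text gives no reasons for leaving and no counts by arm, so neither statement can be made.

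At an assumed 60% rate, one dissatisfied leaver shifts the result by 4.3 points on placebo or 2.1 points on an active arm. With all 3 possible unrated subjects in one arm, the outer limits are 12 points down or 8 up on placebo, and 6 down or 4 up on an active arm. The primary analysis is unaffected.

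**What to change.** 1. **Collection, only if subjects are still on treatment.** Add the single rating item to the Early Discontinuation assessments for subjects exiting before Visit 6, and not to Visit 7 for completers. The Table 4 window needs no change. These subjects already complete the NAVQ at that visit, so the burden is one question. Because it changes the schedule of assessments, it is a protocol amendment needing IRB/IEC approval (protocol Section 10.1.1). SAP Section 10.2 cites a masked disposition review, so it may be too late for this step.

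2. **Analysis, in any case.** In SAP Section 8.3.2 keep the observed-case table, report the number of FAS subjects not rated by arm, and add one supplementary row with all FAS subjects as denominator, counting no rating as not satisfied. Specify this before unmasking. It costs one table row and a sentence of text. Label the row as conservative, since it also counts administrative misses as not satisfied.

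3. **Consistency.** Reconcile protocol Section 7.1 with the Section 8.1.7 note, so that it is clear whether a subject who stops study medication is still expected at Visit 6.
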